14 POTENTIAL BENEFITS TO SUBJECTS

Based on the results of pre-clinical and clinical studies, the addition of nivolumab to standard NY-ESO-1 vaccine/decitabine may improve T cell immune response to NY-ESO-1 vaccination in MDS/AML patients.

15 DATA AND SPECIMEN BANKING

As this is a Phase 1 study, the secondary endpoints are entirely correlative and designed to determine if CDX-1401/poly ICLC in combination with nivolumab and decitabine can induce anti-NY-ESO1 specific immune responses. If these responses are observed in the absence of toxicity, the data will be used to justify a larger study to determine the efficacy of the combination in patients with MDS.

Patients will be sampled serially in this trial in order to determine the degree to which MDS patients treated with decitabine develop NY-ESO-1 promoter hypomethylation and induce NY-ESO-1 mRNA and/or protein expression in circulating myeloid cells. The induction of global and gene specific hypomethylation has been repeatedly documented in patients with MDS and AML treated with hypomethylating drugs (4, 17, 72). We and others have shown that decitabine treatment induces NY-ESO-1 as well as a variety of other CTAs in circulating blasts (Figure 1),(17, 18) and furthermore that such induction of gene expression can be immunogenic (49, 73). In our previous study combining NY-ESO-1 vaccination with decitabine in MDS patients we demonstrated induction of NY-ESO-1 mRNA in circulating CD11b myeloid cells (See Figure 1). We further showed that the cell free DNA compartment recapitulates the methylation signature in circulating cells. In this study samples will be analyzed to confirm induced expression of NY-ESO-1 mRNA in circulating CD11b selected cells. Cell free DNA will be used to assess changes in methylation status at the LINE-1 and NY-ESO-1 promoters. These data will be correlated with observations of NY-ESO-1 specific immune responses.

For subjects enrolled at the Roswell Park Cancer Institute, if a subject does not have enough sampled peripheral blood taken at any time point to conduct these studies, we will add to that by using samples that subject has on hand in the Roswell Park Hematologic Procurement Facility.

Subjects enrolled at RPCI have signed a separate consent for the taking, storage, and future research upon these samples under protocol CIC 98-05.

16 MEASUREMENT OF EFFECT

Objective responses will be recorded and graded at the end of every 4th cycle of treatment using the modified International Working Group Criteria for MDS and AML patients as detailed in **Appendix D**, **Appendix E** and **Appendix F**. Molecular assessment of measurable residual disease (using accrued blood and/or bone marrow samples) will be assessed serially in a retrospective fashion in collaboration with [name] at the National Institutes of Health.

PROTOCOL TITLE: I 49217 - Phase 1 CDX-1401/ Poly-ICLC +Decitabine +Nivolumab in Patients with MDS or Low Blast Count AML

Samples will be sent de-identified to [name] laboratory and results will be reviewed and analyzed by the study team and correlated with immunological response to therapy.

17 SAFETY EVALUATION

17.1 Adverse Events

An adverse event or adverse experience (AE) is any untoward medical occurrence associated with the use of a drug in humans, whether or not considered drug related. Therefore, an AE can be ANY unfavorable and unintended sign (including an abnormal laboratory finding), symptom, or disease temporally associated with the use of a medicinal (investigational) product, whether or not considered related to the medicinal (investigational) product (attribution of 'unrelated', 'unlikely', 'possible', 'probable', or 'definite').

An AE is considered "unexpected" if it is not listed in the investigator brochure or is not listed at the specificity or severity that has been observed; or if an investigator brochure is not required or available, is not consistent with the risk information described in the general investigational plan in other study-related documents.

17.1.1 Diagnosis Versus Signs and Symptoms

If known, a diagnosis should be recorded on the CRF rather than individual signs and symptoms (e.g., record only liver failure or hepatitis rather than jaundice, asterix, and elevated transaminases). However, if a constellation of signs and/or symptoms cannot be clinically characterized as a single diagnosis or syndrome at the time of reporting, each individual event should be recorded as an AE or SAE on the CRF. If a diagnosis is subsequently established, it should be reported as follow-up information.

17.1.2 Adverse Events Occurring Secondary to Other Events

In general, AEs occurring secondary to other events (e.g., cascade events or clinical sequelae) should be identified by their primary cause. For example, if severe diarrhea is known to have resulted in dehydration, it is sufficient to record only diarrhea as an AE or SAE on the CRF. However, clinically significant AEs occurring secondary to an initiating event that are separated in time should be recorded as independent events on the CRF. For example, if a severe gastrointestinal hemorrhage leads to renal failure, both events should be recorded separately on the CRF.

17.1.3 Abnormal Laboratory Values

Only clinically significant laboratory abnormalities that require active management will be recorded as AEs or SAEs on the CRF (e.g., abnormalities that require study drug dose modification, discontinuation of study treatment, more frequent follow-up assessments, further diagnostic investigation, etc.).

If the clinically significant laboratory abnormality is a sign of a disease or syndrome (e.g., alkaline phosphatase and bilirubin 5 x the upper limit of normal associated with cholecystitis), only the diagnosis (e.g., cholecystitis) needs to be recorded on the Adverse Event CRF. If the clinically significant laboratory abnormality is not a sign of a disease or syndrome, the abnormality itself

PROTOCOL TITLE: I 49217 - Phase 1 CDX-1401/ Poly-ICLC +Decitabine +Nivolumab in Patients with MDS or Low Blast Count AML

should be recorded as an AE or SAE on the CRF. If the laboratory abnormality can be characterized by a precise clinical term, the clinical term should be recorded as the AE or SAE. For example, an elevated serum potassium level of 7 mEq/L should be recorded as “hyperkalemia”.

Observations of the same clinically significant laboratory abnormality from visit to visit should not be repeatedly recorded as AEs or SAEs on the CRF, unless their severity, seriousness, or etiology changes.

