10.3 Definition of Dose-Limiting Toxicity

Dose limiting toxicities (DLTs) are defined as any non-hematologic grade 4/5 toxicities that are definitely, probably, or possibly related to the administration of the investigational agent(s) (see Appendix H for organ specific auto-immune grading of toxicity).

All AEs will be graded according to the NCI-CTCAE scale Version 4.0.

Hematological toxicities are expected in patients with MDS undergoing therapy with decitabine and will not be considered dose limiting. Hematological toxicities will not be deemed dose limiting, in agreement with other studies in patients with MDS and AML.

The initial DLT period will be defined as 28 days after the first dose of decitabine. Given that toxicities related to checkpoint inhibitors may not be immediately manifested, after the first 3 patients have been enrolled, accrual to the expansion cohort will be delayed to monitor for late developing toxicities until all patients in the first 3 patient cohort have been followed until cycle 4 day 29 of decitabine.

Patients will be monitored throughout the study and according to the schedule of procedures and observations. Any auto-immune related events which occur between days 29 and the end of study may be sufficient to interrupt the nivolumab therapy if they are grade 4 or 5 as described below. Patients may be withdrawn from study even if DLT is due to decitabine alone.

Safety monitoring will include careful assessment and appropriate reporting of adverse events, as well as the construction and implementation of a data and safety-monitoring plan (Auditing, Monitoring and Inspecting). Medical monitoring will include a regular assessment of the number and type of serious adverse events. As this is a phase I study, all AEs will be reviewed by the Early Phase Clinical Trials committee at RPCI on a weekly basis.

Management and dose modifications associated with the above AEs are outlined in Section 10.3 and Appendix H.

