17.3 Reporting Adverse Events

Routine AEs occurring between the start date of intervention until 180 days after the last intervention, or until the event has resolved, the study participant is lost to follow-up, the start of

PROTOCOL TITLE: I 49217 - Phase 1 CDX-1401/ Poly-ICLC +Decitabine +Nivolumab in Patients with MDS or Low Blast Count AML

a new treatment, or until the study investigator assesses the event(s) as stable or irreversible, will be reported. New information will be reported after it is received.

Guidelines for Routine Adverse Event Reporting for Phase 1 Studies (Regardless of Expectedness)

Attribution	Grade 1	Grade 2	Grade 3	Grade 4
Unrelated	X	X	X	X
Unlikely	X	X	X	X
Possible	X	X	X	X
Probable	X	X	X	X
Definite	X	X	X	X

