19.5.1 Adverse Event

The frequency of toxicities will be tabulated by grade across all dose levels and cycles. The frequency of toxicities will also be tabulated for the dose estimated to be the MTD/MAD. All participants who receive any study treatment will be considered evaluable for toxicity.

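### Laboratory toxicity rates depend on investigator management decisions, because 17.1.3 filters what becomes an AE and Section 19 does not analyse the scheduled chemistry; a narrow DLT ambiguity follows

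*Combined protocol and SAP*

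**What the plan says.** **What becomes an AE.** Section 17.1 is broad: "an AE can be ANY unfavorable and unintended sign (including an abnormal laboratory finding), symptom, or disease temporally associated with the use". The table in 17.3 marks grades 1 to 4 for routine reporting at every attribution, from unrelated to definite.

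**What is entered for laboratory values.** Section 17.1.3 is narrower: "Only clinically significant laboratory abnormalities that require active management will be recorded as AEs or SAEs on the CRF". Its examples of active management are wide: "abnormalities that require study drug dose modification, discontinuation of study treatment, more frequent follow-up assessments, further diagnostic investigation, etc". A significant abnormality that signals a disease or syndrome is replaced on the form by the diagnosis. For the other case the text begins "If the clinically significant laboratory abnormality is not a sign of a disease or syndrome, the abnormality itself" and goes on to require that it be entered as the event.

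**What is a DLT.** Section 10.3: "Dose limiting toxicities (DLTs) are defined as any non-hematologic grade 4/5 toxicities that are definitely, probably, or possibly related" to the investigational agents. Hematologic toxicity is excluded. Laboratory values are not, and there is no management condition.

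**What is analysed.** Section 19.2 quantifies the primary safety objective from observed AE, SAE and DLT rates with one-sided 95% Jeffreys upper limits. Section 19.5.1: "The frequency of toxicities will be tabulated by grade across all dose levels and cycles". Section 19.1 makes the DLT proportion in the 12-patient expansion cohort the primary statistical endpoint. No part of Section 19 grades or tabulates laboratory results as such.

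**What is measured.** Section 11.4 schedules a metabolic panel, LDH, uric acid, amylase and lipase weekly in cycles 1-4, and on day 1 of each cycle from cycle 5.

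**The concern.** A laboratory result passes two investigator judgements before it can enter a toxicity rate: that it is clinically significant, and that it needs action. Restricting AE entry in this way is a common convention. It does little harm when the laboratory data are also graded and tabulated directly. Here they are not, so the AE form is the only stated path from a chemistry result to the safety tables.

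The values most likely to be lost are mild and unmanaged. In a Phase 1 combination with a checkpoint inhibitor, the frequency of mild liver and pancreatic enzyme changes is part of what the safety description should convey. Two investigators facing the same value could also produce different recorded rates.

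A second, smaller issue is that 10.3 and 17.1.3 do not use the same test. A related, asymptomatic grade 4 chemistry value meets 10.3. If it is judged not clinically significant, 17.1.3 does not require it to be entered. The text also does not say which grade 10.3 uses when a diagnosis has replaced the value.

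**Working it through.** **1. The plan's own DLT rule.** Section 19.1 calls therapy too toxic if the upper one-sided 95% Jeffreys limit exceeds 0.60, and says this means 5 or more of 12. The limit is the 95% quantile of Beta(x + 0.5, n - x + 0.5).

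- 4/12: Beta(4.5, 8.5) gives 0.569, below 0.60.
- 5/12: Beta(5.5, 7.5) gives 0.648, above 0.60.

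The cut-off reproduces. The stated 80% at a true rate of 0.27 also reproduces: P(X ≤ 4 of 12) = 0.798. The rule is arithmetically sound, but it presumes that every DLT is recorded.

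**2. How far laboratory AE rates could move.** Table 2 in Section 2.2 reports LFT elevation in 8 of 9 patients in the predecessor study, none at grade 3 or above. Scaled to this trial, 8/9 × 18 = 16 patients.

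- All 16 recorded: 16/18, Beta(16.5, 2.5), upper limit 0.967.
- None recorded: 0/18, Beta(0.5, 18.5), upper limit 0.100.

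This is a limiting case, not an estimate. It requires that none of the 16 patients had a repeat test, a work-up or a dose hold. The input is also uncertain: the narrative in 2.2 on the same nine patients lists liver enzyme elevation at grade 3, which does not agree with Table 2.

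**3. What one unrecorded DLT would do.**

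| Stage | All recorded | One missed | Effect |
|---|---|---|---|
| Dose Level 1 (Table 4) | 2/6 | 1/6 | de-escalate becomes declare the MAD |
| Expansion (19.1) | 5/12, limit 0.648 | 4/12, limit 0.569 | too toxic becomes not too toxic |

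**4. Sensitivity to an assumed missed share.** The documents give no figure for the share m of true DLTs that goes unrecorded. The recorded rate is taken as p(1 - m). Passing the lead-in is P(0 or 1 of 6) = q^6 + 6pq^5, with the recorded rate as p and q = 1 - p. Being called too toxic is P(X ≥ 5 of 12).

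| True rate | Quantity | m = 0 | m = 0.10 | m = 0.25 |
|---|---|---|---|---|
| 0.40 | pass lead-in | 0.233 | 0.301 | 0.420 |
| 0.40 | called too toxic | 0.562 | 0.446 | 0.276 |
| 0.60 | called too toxic | 0.943 | 0.874 | 0.696 |

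Given the other routes to recording, m = 0.25 is a stress value and not a plausible expectation. The table shows how sensitive the rules are. It does not show that DLTs will be missed.

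**The case against.** A reader might infer that grade 4 DLTs will routinely drop out of the primary analysis. The documents do not support that, for four reasons.

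- The examples in 17.1.3 include extra follow-up and further diagnostic work. A related grade 4 chemistry value that prompts even a repeat test meets them.
- Section 10.4.3 and Table 7 withhold or stop nivolumab at moderate liver and creatinine thresholds, at a first other grade 3 reaction, and at grade 4. Each is active management, so most nivolumab-attributed signals are entered well below grade 4.
- Section 10.5 says an unscheduled visit should follow an AE considered possibly related to study drug. A DLT must be at least possibly related, so this route applies whichever agent is blamed.
- The network-site instructions (item 7, Serious Adverse Event Reporting) provide a memo for potential DLTs, Section 8.1 says AEs and DLTs will be collected, and Section 6 requires patients' results or records to be reviewed every two weeks.

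All four stand, and they reduce the DLT issue to a small residue: a related, asymptomatic grade 4 value that the investigator judges not clinically significant and does not act on. Section 10.5 helps only once someone regards the value as an AE, and the memo is described only for network sites.

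It can also be said that 17.1 states what may be an AE while 17.1.3 sets the recording convention, so the two do not flatly contradict each other. That is fair as a reading. It does not change the result: the rates in 19.2 are rates of what was recorded, and none of the four routes brings in low-grade values below the Table 7 thresholds that nobody acts on.

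**Conclusion.** The concern holds in a limited form. The laboratory toxicity rates in 19.2 and 19.5.1 are conditional on management decisions, and nothing in Section 19 compensates. The understatement falls mainly on low-grade, unmanaged abnormalities. Its size cannot be derived from the documents; 0/18 against 16/18 marks the outer limit and rests on a Table 2 entry that the accompanying narrative contradicts.

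For DLTs, 10.3 and 17.1.3 are inconsistent at one narrow point. The consequence of a single missed event is large because the samples are 6 and 12, but the probability of a miss is unknown and probably small. The stronger inference, that isolated grade 4 values are generally lost, is not supported, and any figure for the share missed is an assumption. Hematologic values are unaffected, since they never count as DLTs.

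Severity is minor, and the point is worth making because the remedy is cheap.

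**What to change.** 1. In 19.5.1, add a table of worst post-baseline CTCAE v4 grade per patient against baseline grade. Derive it from all protocol-scheduled laboratory results, whether or not an AE was entered. Confirm that these results are captured in the eCRF, since Section 18.1 does not list them.
2. Reconcile 17.1, 17.1.3, 17.3 and 10.3. They should state whether a related non-hematologic grade 4 laboratory value goes to DLT review regardless of management, and which grade applies when a diagnosis replaces the value. The choice of rule is the sponsor's; what matters is that the sections agree.

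The cost is one extra table, a few sentences and some data handling. Reported laboratory toxicity rates will probably look somewhat less favourable.

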17.1.4 Preexisting Medical Conditions (Baseline Conditions)

A preexisting medical condition should be recorded as an AE or SAE only if the frequency, severity, or character of the condition worsens during the study. When recording such events on an Adverse Event CRF, it is important to convey the concept that the preexisting condition has changed by including applicable descriptors (e.g., “more frequent headaches”).

17.2 Grading and Relationship to Drug

The descriptions and grading scales found in the CTEP Version 4 of the NCI Common Terminology Criteria for Adverse Events (CTCAE) will be utilized for AE reporting. CTEP Version 4 of the CTCAE is identified and located at:

http://ctep.cancer.gov/protocolDevelopment/electronic_applications/ctc.htm.

AEs not covered by specific terminology listed should be reported with common medical terminology, and documented according to the grading scales provided in the CTCAE Version 4.

The relationship of event to study drug will be documented by the Investigator as follows:

- **Unrelated:** The event is clearly related to other factors such as the participant’s clinical state, other therapeutic interventions or concomitant drugs administered to the participant.
- **Unlikely:** The event is doubtfully related to investigational agent(s). The event was most likely related to other factors such as the participant’s clinical state, other therapeutic interventions, or concomitant drugs.
- **Possible:** The event follows a reasonable temporal sequence from the time of drug administration, but could have been produced by other factors such as the participant’s clinical state, other therapeutic interventions or concomitant drugs.
- **Probable:** The event follows a reasonable temporal sequence from the time of drug administration, and follows a known response pattern to the study drug. The event cannot be reasonably explained by other factors such as the participant’s clinical state, therapeutic interventions or concomitant drugs.
- **Definite:** The event follows a reasonable temporal sequence from the time of drug administration, follows a known response pattern to the study drug, cannot be reasonably explained by other factors such as the participant’s condition, therapeutic interventions or concomitant drugs; AND occurs immediately following study drug administration, improves upon stopping the drug, or reappears on re-exposure.

17.3 Reporting Adverse Events

Routine AEs occurring between the start date of intervention until 180 days after the last intervention, or until the event has resolved, the study participant is lost to follow-up, the start of

PROTOCOL TITLE: I 49217 - Phase 1 CDX-1401/ Poly-ICLC +Decitabine +Nivolumab in Patients with MDS or Low Blast Count AML

a new treatment, or until the study investigator assesses the event(s) as stable or irreversible, will be reported. New information will be reported after it is received.

Guidelines for Routine Adverse Event Reporting for Phase 1 Studies (Regardless of Expectedness)

Attribution	Grade 1	Grade 2	Grade 3	Grade 4
Unrelated	X	X	X	X
Unlikely	X	X	X	X
Possible	X	X	X	X
Probable	X	X	X	X
Definite	X	X	X	X

17.4 Serious Adverse Events

A serious adverse event (SAE) is any adverse event (experience) that in the opinion of either the investigator or supporter results in **ANY** of the following:

- Death.
- A life-threatening adverse event (experience). Any AE that places a participant or participants, in the view of the Investigator or supporter, at immediate risk of death from the reaction as it occurred. It does NOT include an AE that, had it occurred in a more severe form, might have caused death.
- Inpatient hospitalization or prolongation of existing hospitalization (for > 24 hours).
- A persistent or significant incapacity or substantial disruption of the ability to conduct normal life functions.
- A congenital anomaly or birth defect.
- Important Medical Event (IME) that, based upon medical judgment, may jeopardize the participant and may require medical or surgical intervention to prevent one of the outcomes listed above.

17.4.1 Reporting Serious Adverse Events

All new SAEs related to study procedures occurring from the date the participant signs the study consent until the start date of intervention or date of screen fail will be reported. All new SAEs occurring from the start date of intervention until 180 days after the last intervention or a new treatment is started, whichever comes first, will be reported. The RPCI SAE Source Form is to be completed with all available information, including a brief narrative describing the SAE and any other relevant information.

SAEs occurring after the 180 day follow-up period that the investigator determines to be possibly, probably or definitely related to the study intervention should be reported.

SAEs identified as an Unanticipated Problem by the Investigator must be reported. Please refer to **Section 17.7** for details on reporting Unanticipated Problems.

PROTOCOL TITLE: I 49217 - Phase 1 CDX-1401/ Poly-ICLC +Decitabine +Nivolumab in Patients with MDS or Low Blast Count AML

17.5 Investigator Reporting: Notifying the Study Supporter

All Serious Adverse Events (SAEs) that occur following the subject's written consent to participate in the study through 30 days of discontinuation of dosing must be reported to BMS Worldwide Safety, whether related or not related to study drug. If applicable, SAEs must be collected that relate to any later protocol-specified procedure (e.g., a follow-up skin biopsy).

Follow-up safety evaluations will occur 30 days (\pm 3 days), 60 days (\pm 3 days), 90 days (\pm 3 days), and 180 days (\pm 3 days) after last dose of study drug (last immunization with CDX-1401/poly ICLC/nivolumab) .or until resolution of any drug-related toxicity. Assessment may be collected via telephone if the patient elects to come off study and is no longer coming to clinic.

- Following the subject's written consent to participate in the study, all SAEs, whether related or not related to study drug, are collected, including those thought to be associated with protocol-specified procedures. The investigator should report any SAE occurring after these aforementioned time periods, which is believed to be related to study drug or protocol-specified procedure.
- An SAE report should be completed for any event where doubt exists regarding its seriousness.
- If the investigator believes that an SAE is not related to study drug, but is potentially related to the conditions of the study (such as withdrawal of previous therapy or a complication of a study procedure), the relationship should be specified in the narrative section of the SAE Report Form.

Investigators MUST report within 1 business day upon becoming aware, to the supporter ANY Serious Adverse Events, whether or not they are considered related to the investigational agent(s)/intervention.

The investigator must inform Bristol Myers Squibb (BMS) and Celldex in writing using a BMS SAE form or MEDWATCH 3500A form of any SAE within 24 hours of being aware of the event. The written report must be completed and supplied to Celldex by facsimile within 24 hours/1 business day.

- The BMS protocol ID number must be included on whatever form is submitted by the Sponsor/Investigator.

The initial report must be as complete as possible, including an assessment of the causal relationship between the event and the investigational product(s), if available. Information not available at the time of the initial report (e.g., an end date for the adverse event or laboratory values received after the report) must be documented on a follow-up report.

Celldex and BMS consider an SAE to be any adverse event that is life-threatening or that results in any of the following outcomes: death; inpatient hospitalization or prolongation of existing hospitalization; persistent or significant disability or incapacity; or a congenital anomaly or birth defect.

PROTOCOL TITLE: I 49217 - Phase 1 CDX-1401/ Poly-ICLC +Decitabine +Nivolumab in Patients with MDS or Low Blast Count AML

Completed SAE reports are to be submitted to:

Bristol-Myers Squibb
SAE Email Address: [contact]
SAE [contact]

AND

Celldex Therapeutics, Inc.
Clinical Research/Operations
[contact]
[contact]
Email: [contact]

